1.0 Introduction

This documentation describes the planned data analyses for clinical study IVC-400-006 sponsored by Mindset Medical, LLC.

This SAP supersedes the statistical considerations identified in the protocol; where considerations are substantially different, and these differences will be identified. If additional analyses are required to supplement objectives described in the SAP, they may be performed and will be identified in the Clinical Study Report (CSR) or through an SAP addendum (as warranted).

Analyses described in the current SAP version is based on the protocol version 1 IVC-400-006 dated March 31, 2023.

2.0 Study Objectives and Endpoints

2.1 Study Objective

The primary objective of the study is to establish that pulse rate (PR) measured with the IVC App are accurate to within +/- 3 BPM ARMS (average root mean square) of Heart Rate (HR) measured with the reference ECG device.

2.1.1 Primary Endpoint

The primary endpoint is a non-inferiority comparison to an FDA approved reference device to establish that PR measured with the IVC App are accurate to an ARMS of +/- 3 BPM. In accordance with ISO 80601-2-61:2017(E) accuracy will be calculated as the RMS difference between the IVC App and the heart rate measured by the ECG reference device.

3.0 Study Hypothesis

The IVC App can measure pulse rate between 50 and 130 BPM to an accuracy of +/-3 BPM average RMS. The hypothesis will be tested in a non-inferiority design. PR will be collected simultaneously with the IVC App and HR with an ECG reference device, and the ARMS and its 95% confidence interval calculated. If the upper limit of the 95% confidence interval of the ARMS is < 3.0, the IVC App will be determined to be non-inferior and the hypothesis that it is accurate to an ARMS of +/- 3.0 accepted.

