30	31	1	2	3	4	5																																												
4.	
From the Select PROs drop down menu, select IVC-PR-CLINICAL-STUDY.
 																																																	
5.	
Click the Send PRO Request(s) button to send the IVC-PR-CLINICAL-STUDY to the mobile phone. The message will be sent to the Google Voice Messaging App on the Mobile Device.
 																																																	

INFORMED MINDSET MEDICAL	DOCUMENT VERSION: 1	THIS DOCUMENT SUPERSEDES VERSION: X	PAGE:
STATUS: Active	TITLE: Informed Vital Core –Clinical Study Instruction Guide: Pulse Rate	IDENTIFICATION: IVC-400-006g	14 OF 25
EFFECTIVE DATE: April 5, 2023	AUTHOR: [name]	APPROVED BY: [name]	

[figure not shown]
7. Preparing the IVC App for PR Measurement

Step	Task
1.	Ensure the subject has been sitting comfortably for 5 minutes, positioned behind a table of normal height with their back pressed against the seat rest, their feet flat on the floor, legs uncrossed, and their face uniformly lit with the light in front of the subject.
2.	Tap on the Google Voice App on the mobile phone. 
3.	Tap the link contained in the SMS Message.  Note: the text message may take a few minutes to be sent from the system to the phone.
4.	
4.	When the Chrome mobile web browser is opened, tap and enter 01/01/2000 into the DOB confirmation field.  Tap the Continue button.
5.	Tap the Start button.

INFORMED MINDSET MEDICAL	DOCUMENT VERSION: 1	THIS DOCUMENT SUPERSEDES VERSION: X	PAGE:
STATUS: Active	TITLE: Informed Vital Core –Clinical Study Instruction Guide: Pulse Rate	IDENTIFICATION: IVC-400-006g	15 OF 25
EFFECTIVE DATE: April 5, 2023	AUTHOR: [name]	APPROVED BY: [name]	

Step	Task
	
6.	 
Tap the Next button.

7.	
Make sure the subject is still and tap the PREVIEW button to capture an image of the subject.
 
 • Subject should remain still – no talking, head movement, fidgeting • Subject's face should be well lit with lighting in front • No movement behind the subject, TV screens, ceiling fans, or people walking • Minimize shadows including ones cast from eyeglasses on the cheeks • No hats, do-rags, masks, the forehead, cheeks, and chin need to be visible • Heavy bangs and hair should be pulled away from the face

INFORMED MINDSET MEDICAL	DOCUMENT VERSION: 1	THIS DOCUMENT SUPERSEDES VERSION: X	PAGE:

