4.2.4 Endpoint Variables

The endpoint variables are the IVC App PR and ECG reference device HR.

Summary statistics of the HR and PR measured for each device within the PP group will be tabulated and reported as described in section 5.2.2.

Subjects in the PP group will be tabulated by IVC App PR in groups of 10 bpm and the number of subjects and percentages in each pulse rate group reported.

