5.2 General Considerations

5.2.1 Listings

All study data will be included in the study data listings. Both the captured data and the MedDRA and WHO Drug codes will be provided. Listings will be displayed by subject in chronological order, if not stated otherwise.

Study data will be provided in electronic format, either as SAS XPT V5 files or CSV files.

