5.2.2 Descriptive Statistics and Summary Tables

The total number of subjects in the study group (N) under the stated population will be displayed in the header of summary tables.

For age, height, weight, and BMI, the mean, standard deviation, minimum and maximum will be presented along with the n size from which the statistics were calculated.

PR and HR data will be presented as median, lower, and upper quartiles, min, max, and n size because they were not normally distributed in product development data (5.1.4).

For categorical variables, count, and percentage of subjects/counts in each device group and/or category will be presented. Percentages will be based on number of subjects with non-missing values, if not specified otherwise.

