5.3 Endpoint Data Analysis Methods

5.3.1 Primary Endpoint

For the primary endpoint analysis, the ARMS will be calculated as the square root of the mean difference between the devices, as described in ISO 80601-2-61:2017(E). All PP subjects will be included in the primary endpoint analysis. The 95% CI for the primary endpoint analysis will be determined by jackknifing 100,000 samples with replacement and calculating a 95% CI from the distribution of ARMS among the jackknifed samples. If the ARMS and its upper 95% confidence interval are below the target of 3.0, the device will be determined to be non-inferior.

 INFORMED MINDSET MEDICAL	DOCUMENT VERSION: 3	THIS DOCUMENT SUPERSEDES VERSION: 2	PAGE: 12 OF 15
STATUS: Active	TITLE: Informed Vital Core - Statistical Analysis Plan	IDENTIFICATION: IVC-400-006d	
EFFECTIVE DATE: June 22, 2023	AUTHOR: [name]	APPROVED BY: [name]	

A Bland-Altman plot will be constructed from the differences vs. the average measured PRs and HRs for all PP subjects to assist in visualizing the differences between devices and the full range of PR and HR measurements. Since the differences were not normally distributed due to the “white coat” effect on PR in the product development data, upper and lower 95th percentiles will be drawn on the graph to aid in visualization rather than two standard deviations. Visible outliers with greater than +/- 6.0 BPM difference from the reference device will be tabulated. A threshold of +/- 6.0 BPM will be considered outlying because under a labelled ARMS of +/- 3.0, 95% of the differences should fall in the range of +/- 6.0 BPM against the reference.

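### SAP 3.0 states accuracy for 50–130 BPM, but nothing in the readable text ties the pooled ARMS conclusion to the heart rates observed

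*Combined protocol and SAP*

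**What the plan says.** SAP 3.0 puts the hypothesis as "The IVC App can measure pulse rate between 50 and 130 BPM to an accuracy of +/-3 BPM average RMS". It then accepts the hypothesis if the upper 95% limit of the ARMS is below 3.0. SAP 5.3.1 repeats the rule: "If the ARMS and its upper 95% confidence interval are below the target of 3.0, the device will be determined to be non-inferior". All PP subjects enter that single ARMS. The objective (2.1) and the endpoint (2.1.1) give the 3 BPM target without naming a range.

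On measurement conditions, the Clinical Study Instruction Guide, Section 7, step 1, reads: "Ensure the subject has been sitting comfortably for 5 minutes". The readable eligibility criteria contain no heart-rate criterion. The only readable target for the make-up of the PP group is the 15% for Fitzpatrick 5–6 in SAP 6.2.

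On reporting by rate, SAP 4.2.4 says: "Subjects in the PP group will be tabulated by IVC App PR in groups of 10 bpm", as counts and percentages. Other planned output:

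- 5.2.2: "PR and HR data will be presented as median, lower, and upper quartiles, min, max, and n size".
- 5.3.1: a Bland-Altman plot, and "Visible outliers with greater than +/- 6.0 BPM difference from the reference device will be tabulated".
- 5.2.1: "All study data will be included in the study data listings".
- 1.0: "If additional analyses are required to supplement objectives described in the SAP, they may be performed".

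**The concern.** The hypothesis covers an interval of rates, while the rule that accepts it looks only at the average size of the error in whoever was measured. A PP group made up wholly of people at resting rates could meet the rule. The SAP as written would then accept a hypothesis that names 50–130 BPM, with few or no observations in part of that interval.

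The one table organised by rate does not close the gap. It gives counts without accuracy, and it sorts subjects by the device under test. A subject whom the App misreads by enough to cross a band limit is counted in the wrong band. That is least helpful exactly where the table would matter.

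What is at stake is the wording of the conclusion. The validity of the pooled test is not in question.

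**Working it through.** **Step 1: set the passages side by side.**

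| Place | Names 50–130 BPM? | Depends on the rates observed? |
|---|---|---|
| SAP 2.1, 2.1.1 (objective, endpoint) | No | No |
| SAP 3.0, opening sentence | Yes | No |
| SAP 3.0, acceptance sentence | No, but it accepts the hypothesis just stated | No |
| SAP 5.3.1, decision | No | No; all PP subjects pooled |
| SAP 4.2.4, table | No | Shows counts by App PR; not part of the decision |
| SAP 5.2.2 and 5.3.1, descriptive output | No | Shows the range; not part of the decision |

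One further passage might bear on range. The note at the end of Section 4.2 of the Rhythm Strip Analysis Procedure says the script warns when a reference range conflicts with the protocol. The range is not explained. It could be the 15 BPM within-session limit of SAP 4.1.4, or a rule in redacted text. As described, the warning may go to a notes field and does not enter the decision.

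**Step 2: how much of the claimed range could be thin?** The SAP gives no figure for coverage, so there is none to reproduce. Its power figures (40 subjects for 90%, 45 for 95%, at an ARMS of 1.5) come from development differences that the documents do not contain. They cannot be reproduced and are not needed here.

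The part above 100 BPM is (130 − 100)/(130 − 50) = 30/80, or three of the eight 10-bpm bands. The PP goal is n = 55 (SAP 6.2). The share p of subjects above 100 BPM is not in the documents, so 1% to 5% is an assumption. Expected number = n·p; chance of none = (1 − p)^n.

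| Assumed p | Expected among 55 | Chance of none |
|---|---|---|
| 1% | 0.55 | 0.99^55 = 57.5% |
| 2% | 1.10 | 0.98^55 = 32.9% |
| 3% | 1.65 | 0.97^55 = 18.7% |
| 5% | 2.75 | 0.95^55 = 6.0% |

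If App non-reporting were the only loss, 85 enrolled × 0.805 = 68.4, so about 68 PP subjects. The two ends become 0.99^68 = 50% and 0.95^68 = 3%.

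A different assumption shows how far this depends on p. Take seated heart rate as normal with mean/SD 68/10, 72/12, 76/13 or 80/14 (also not from the documents). The expected number above 100 BPM among 55 is then 0.04, 0.54, 1.78 or 4.21. The chance of nobody above 110 BPM is 99.9%, 96%, 78% or 41%.

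**Step 3: binning.** Suppose, hypothetically, that the ECG shows 105 BPM and the App reads 8 BPM low, at 97. The 4.2.4 table counts that subject in the 90–99 band, and the 100–109 band loses its observation. The opposite error would add a subject to a band that the ECG does not support. When the App is accurate, few subjects move.

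**The case against.** The case on the other side is substantial.

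- **The accepted conclusion may be narrower.** The range appears once, in the opening sentence of 3.0; the acceptance sentence and 5.3.1 omit it. This stands to the extent that the defect may be only an ambiguity. Still, the acceptance sentence refers to the hypothesis, and the only one stated in 3.0 carries the range.
- **Redaction.** The protocol's hypothesis, endpoint and sample-size text, and parts of its design and procedures, cannot be read. A coverage rule may sit there. This stands, and it limits confidence. But SAP 1.0 says the SAP supersedes the protocol's statistical considerations, and the SAP's own decision rule refers to no such condition.
- **The information is already planned.** Heart-rate minimum, maximum and quartiles, the Bland-Altman plot, the table of differences beyond 6 BPM and full listings would show a careful reader where data are thin. This stands: nothing would be hidden. None of it restricts what is concluded.
- **Seated rest does not prove a thin range.** Recruitment includes hospitals and clinics, and the SAP describes a white-coat effect on pulse rate. This also stands. The coverage figures are assumptions, and the documents do not report the heart rates in the development data.

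A reader might go further and infer that the pooled rule would wrongly pass an App that fails at high rates. The documents do not support that. With three of 55 subjects misread by 6 BPM and the rest at the development ARMS of 0.9 or 1.5, the pooled ARMS is √[(52 × 0.81 + 3 × 36)/55] = 1.65, or √[(52 × 2.25 + 3 × 36)/55] = 2.02. With three misread by 8 BPM it is 2.06 or 2.37. All are below 3.0, so passing would be correct for the endpoint as defined, and nothing in the documents suggests that accuracy is worse at high rates.

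**Conclusion.** The point holds as a minor analysis and reporting improvement. SAP 3.0 names 50–130 BPM. The acceptance rule is one pooled limit, and no readable passage connects the two through the heart rates observed. The only table by rate has no accuracy figure and is sorted by the App's own reading.

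The size of the gap cannot be fixed from the documents. Under the assumed 1% to 5% above 100 BPM, the chance that none of 55 PP subjects falls there is 58% to 6%; other plausible assumptions widen this. The conclusion rests on the readable text only.

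Two broader readings should not be drawn. First, it does not follow that the trial lacks any heart-rate coverage rule, because the relevant protocol text is redacted. Second, a reader might extend the argument to skin tone, since 6.2 sets a 15% target and 4.2.5 excludes subgroup analyses. But 4.2.2 already tabulates the three Fitzpatrick groups, 6.2 gives diversity of the PP group as the purpose, and 4.2.5 states its reason. An accuracy table by skin tone would be a preference; its absence is not a defect.

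**What to change.** 1. **SAP 4.2.4:** form the 10-bpm bands from the ECG reference heart rate. Give n and a descriptive ARMS per band, and list the individual differences where n is very small. Add a line that this table is descriptive and untested, so that it does not collide with 4.2.5.
2. **SAP 3.0 and 5.3.1:** state the pooled conclusion together with the observed ECG heart-rate distribution. Say that accuracy is not shown for bands within 50–130 BPM that have no subjects or fewer than a minimum count. Set that minimum as a number in the SAP before database lock. Without a number, a single subject at 105 BPM would stretch the supported range to 105. If lock has already taken place, label the count as chosen afterwards.

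The cost is SAP wording and one revised table from data already collected. The primary test, the 3.0 margin and the sample size do not change. The downside is that the supported range may turn out narrower than 50–130 BPM, and ARMS in sparse bands will be imprecise.

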4.0 Statistical and Analytical Procedures

4.1 Analysis Populations and Collection Groups

The following populations will be considered for the study:

4.1.1 All-Enrolled Population

The All-Enrolled population will be defined as all subjects who signed the ICF. The number of screen failures and the reasons for failure will be tabulated and reported. Subjects who consent but withdraw before data collection will be tabulated and reported.

 INFORMED MINDSET MEDICAL	DOCUMENT VERSION: 3	THIS DOCUMENT SUPERSEDES VERSION: 2	PAGE: 8 OF 15
STATUS: Active	TITLE: Informed Vital Core - Statistical Analysis Plan	IDENTIFICATION: IVC-400-006d	
EFFECTIVE DATE: June 22, 2023	AUTHOR: [name]	APPROVED BY: [name]	

4.1.2 Intent-to-Capture Population (ITC)

The Intent-to-Capture (ITC) population will be defined as all consented subjects who passed screening and completed at least one data collection session without withdrawing.

4.1.3 Per-Protocol Population (PP)

In order to compare devices, subjects must have a simultaneous PR measurement from the IVC App and an HR measurement from the reference ECG device. Therefore, the Per Protocol analysis group for the primary endpoint will consist of subjects from whom PR measurement from the IVC App and a successful HR data collection from the ECG reference device were collected during the same window.

In preliminary testing of the ECG reference device, not all collections produced a rhythm strip suitable for analysis. The ECG data are processed after the subject's participation in the study ends, so there is no way to detect an unusable ECG collection during the study. In order to increase the likelihood of collecting usable ECG data, two sessions will be collected from each subject.

Subjects will be asked to collect up to 3 additional sessions as technical fallbacks if a collection failure occurs from the reference device or if conditions at the study site interfere with the functionality of the IVC App. Examples of technical difficulties include, but are not limited to, frozen or stuttering video during data capture, failure of the reference device to produce a rhythm strip, connection issues with the reference device, interruptions during data collection that require the subject to leave the camera frame, or upload failures.

4.1.4 Successful Data Collection

ECG rhythm analysis will be performed and calculated using a synchronized moving average across 12-RR intervals as described in IVC-400-006i – Informed Vital Core Heart Rate Rhythm Analysis Procedure. A successful data collection is defined as a session that produces a measurement from the IVC App and the ECG reference device where the moving average of the HR measurement from the reference device does not vary by more than 15 BPM during the 1 minute of measurement. A 15 BPM threshold is applied to the ECG data because variability in contact with the electrodes, subject movement, or atypical ECG waveforms can result in processing artifacts that appear as unrealistically large jumps or fluctuations in HR during the session. In instances where the reference HR is found to vary by more than 15 BPM, the second data collection session will be used for analysis.

The second session will not be treated as a fallback for the IVC App. The study is designed to represent a patient encounter with the IVC App. Under the intended use, if the IVC App cannot collect video from which a PR can be determined after prompts to stop moving or improve lighting, patients are instructed to retry up to twice. If the HR collection with the ECG reference device is successful but the IVC App does not produce a PR, the subject will be excluded from the PP analysis group and considered to be an IVC App collection failure.

All subjects in the ITC group who were not included in the PP group will be listed with the reason they were excluded from the analysis. Subjects will be excluded if the reference device does not collect data, the ECG

 INFORMED MINDSET MEDICAL	DOCUMENT VERSION: 3	THIS DOCUMENT SUPERSEDES VERSION: 2	PAGE: 9 OF 15
STATUS: Active	TITLE: Informed Vital Core - Statistical Analysis Plan	IDENTIFICATION: IVC-400-006d	
EFFECTIVE DATE: June 22, 2023	AUTHOR: [name]	APPROVED BY: [name]	

from both reference device collections is not suitable for rhythm analysis as defined above, or the IVC App does not report a PR during the first session where the ECG collection is successful.

A subject could withdraw before all data collection attempts and technical fallbacks are completed. If the subject has a successful collection, they will still be included in the PP group. Otherwise, they will be excluded from the PP group. If they completed an IVC App collection without a reference HR, that collection will be included when calculating the IVC App success rate as described in section 5.3.2.

4.1.5 Data Collection Groups

Simultaneous data collection from the ECG reference device and IVC App device will be performed on all subjects so there is only one data collection group.

4.2 Analysis Variables

4.2.1 Subject's Disposition and Analysis Sets

Disposition will be summarized descriptively with counts and percentages using the All-Enrolled population for both devices (IVC App and reference device) data collection and all Intent to Collect and all Per Protocol subjects. The number and percentage of subjects who prematurely discontinued from the study along with reasons for study discontinuation will be summarized as well.

A subject's eligibility with inclusion/exclusion criteria failed/met will be listed, along with the list of protocol deviations.

4.2.2 Demographics and Baseline Characteristics

Demographic data and baseline characteristics will include:

- Sex
- Ethnicity
- Race
- Fitzpatrick scale- Fitzpatrick scale skin tones will be grouped into light (Fitzpatrick 1 and 2), medium (Fitzpatrick 3 and 4) and dark (Fitzpatrick 5 and 6).
- Age (years)
- Height (cm)
- Weight (kg)
- BMI (kg/m²)

Demographics and baseline characteristics will be tabulated and summarized as described in section 5.2.2.

The summary results will be based on the ITC population.

4.2.3 Health Conditions and Concomitant Medications

Self-reported health conditions will be coded using MedDRA, tabulated and reported.

Concomitant medications will be coded with WHODrug, tabulated, and reported.

 INFORMED MINDSET MEDICAL	DOCUMENT VERSION: 3	THIS DOCUMENT SUPERSEDES VERSION: 2	PAGE: 10 OF 15
STATUS: Active	TITLE: Informed Vital Core - Statistical Analysis Plan	IDENTIFICATION: IVC-400-006d	
EFFECTIVE DATE: June 22, 2023	AUTHOR: [name]	APPROVED BY: [name]	

The summary results will be based on the ITC population.

4.2.4 Endpoint Variables

The endpoint variables are the IVC App PR and ECG reference device HR.

Summary statistics of the HR and PR measured for each device within the PP group will be tabulated and reported as described in section 5.2.2.

Subjects in the PP group will be tabulated by IVC App PR in groups of 10 bpm and the number of subjects and percentages in each pulse rate group reported.

4.2.5 Subgroup Analysis

No subgroup analyses will be performed, since the study is not powered or sized for subgroup analysis.

4.2.6 Adverse Events (AE)

While adverse events are not anticipated in this clinical study, if the reason for removal of a subject from the study is an adverse event, the event will be recorded on the appropriate eCRF(s) and will be reported to Mindset Medical per the AE reporting guidelines (Required Reporting Timelines per Regulatory Guidance). All efforts will be made to follow the subject until the condition resolves, or the Investigator determines that the subject's health has returned to an acceptable state.

All verbatim AE terms will be coded using the Medical Dictionary for Regulatory Activities (MedDRA) of the latest version and summarized by system organ class (SOC) and preferred term (PT).

An Unanticipated Adverse Device Effect (UADE) is "any serious" adverse effect on health or safety or any life-threatening problem or death caused by, or associated with, a device, if that effect, problem, or death was not previously identified in any nature, severity, or degree of incidence in the investigational plan or any other unanticipated serious problem associated with a device that relates to the rights, safety, and welfare of subjects.

All Life-Threatening AEs will be considered as Severe.

All AEs will be classified in one of two types of relation to device:

- Not Related
- Related (Definitely Related and Possibly Related)

AEs in the ITC population will be tabulated and summarized by type, severity, and MedDRA codes as described in section 5.2.2.

 INFORMED MINDSET MEDICAL	DOCUMENT VERSION: 3	THIS DOCUMENT SUPERSEDES VERSION: 2	PAGE: 11 OF 15
STATUS: Active	TITLE: Informed Vital Core - Statistical Analysis Plan	IDENTIFICATION: IVC-400-006d	
EFFECTIVE DATE: June 22, 2023	AUTHOR: [name]	APPROVED BY: [name]	

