6.3 Safety Analysis

No safety analysis is planned. The IVC App is a remote device so no device related AEs are anticipated.

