Subject ID	MedDRA System Organ Class/ Preferred Term/ Investigator AE Term	Start Date	End Date	Ongoing?	SAE?	Criteria	Severity	Process	Relatio nship	Any	Unanticipated	Caused to Adverse Study Device	Study Discontinu ation
									SAE	Study			
No Data To Report													

ITC = Intent-to-Capture. SAE = Serious Adverse Events.

Program name: 1_16_2_7_1.sas

Run Date: 21NOV2023

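### The AE summary table uses the ITC population, so an adverse event that ends participation before a first completed session is left out of it

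*Combined protocol and SAP*

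**What the plan says.** SAP 4.2.6 names one population for the AE table: "AEs in the ITC population will be tabulated and summarized by type, severity, and MedDRA codes". SAP 4.1.2 defines that population as "all consented subjects who passed screening and completed at least one data collection session without withdrawing", and the protocol (Analysis of the primary endpoint) gives the same definition.

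The SAP has a wider set in 4.1.1: "The All-Enrolled population will be defined as all subjects who signed the ICF". It is used for disposition (4.2.1) but not for AEs. No separate safety population is defined.

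SAP 4.2.6 also provides for AE-related removal: "if the reason for removal of a subject from the study is an adverse event, the event will be recorded". The protocol's Adverse Events section says that AEs will be summarized at each annual renewal for every participating subject.

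SAP 6.3 then states: "No safety analysis is planned".

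**The concern.** Entry to the AE table depends on something that an adverse event can itself prevent, namely finishing a first session. If a subject has an event during preparation but goes on to complete a session, the event is counted. If the same event makes the subject stop, it is not. The events that end participation early are the ones a reader of an AE table would most want to see, and the SAP foresees them.

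In a one-day study where AEs are not expected, the AE table will hold few events or none. One omission can then turn a report of one event into a report of none. The statement in 6.3 adds to the difficulty: read alone, it suggests that no AE summary will be produced, whereas 4.2.6 describes one.

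**Working it through.** The plan gives no AE rate, safety hypothesis or safety sample size, so there is no figure to reproduce. The check is one of set membership.

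**What happens before a first session is complete.** The Clinical Study Instruction Guide describes makeup-removal wipes and medical tape where needed (section 3.1), alcohol cleaning of the forearms and lower leg, shaving of electrode sites where necessary and adhesive electrodes (section 5), and then a 60-second recording. Subjects therefore undergo study procedures before they can enter ITC. That these steps could cause a minor skin event is an inference; the documents do not say so.

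**Where an AE that leads to withdrawal ends up, by timing.**

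- After consent but before any procedure: outside ITC and outside the AE table. The protocol (Withdrawal and Lost to Follow Up) foresees such withdrawals. The subject has had no study exposure, so little is lost.
- After procedures begin but before a first session is complete: outside ITC and outside the AE table. This is the gap.
- After a successful collection: SAP 4.1.4 (last paragraph) keeps the subject in the Per-Protocol group. The same section treats that group as part of ITC, since it lists the ITC subjects who are not in it. The event is in the table.
- After a completed session that was not successful: SAP 4.1.4 counts a completed app collection towards the reporting rate in 5.3.2, and that rate is calculated from ITC. This implies that the subject is in ITC and the event is in the table, although the text does not say so outright.

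**Where an omitted event still appears.** It should be on the eCRF (4.2.6) and in the listings, which are to contain all study data (5.2.1). The reason for discontinuation should be in the disposition summary (4.2.1).

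**Size.** SAP 6.1 and 6.2 give a Per-Protocol target of 55, an app collection rate of 80.5% and an enrolment of 85.

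- Subjects needed for 55 successes: 55 / 0.805 = 68.3, rounded up to 69.
- Remaining allowance: 85 − 69 = 16 for screening failures, withdrawals and technical failures together.

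The SAP does not split the 16, so the number who could fall into the gap cannot be derived. As an illustration only, assume one such event and between 69 and 85 subjects who began a procedure. The table should then show between 1/85 = 1.2% and 1/69 = 1.4%. Under the ITC rule the numerator is 0.

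**The case against.** The strongest reply is that the window is small and little information is lost.

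- **Scope.** A reader might infer that any AE causing withdrawal disappears from the table. The documents do not support this. SAP 4.1.4 keeps subjects who withdraw after a successful collection. Only a literal reading of the ITC definition, under which a subject must never withdraw at all, would remove them, and that conflicts with 4.1.4. This objection stands and limits the point to events before a first completed session.
- **Other reporting.** The event is recorded, listed and reflected in the disposition reasons, and study-related AEs go to the sponsor within 24 hours (protocol, Required Reports). This also stands, but none of it restores the count or the denominator in the table.
- **A sentence without a population.** SAP 4.2.6 also says that AE terms will be coded and summarized by system organ class and preferred term, with no mention of ITC. The text is ambiguous to that extent. ITC is nevertheless the only population the section names.
- **The AE definition.** The protocol counts events from device implantation, which does not fit this study. Read strictly, it might exclude events during preparation. Against that, the protocol wants AEs reported whatever their cause, and the eCRF asks about relationship to the study procedure.
- **The AE listing.** A reader might infer from the footnote to the listing at the end of the combined document ("ITC = Intent-to-Capture. SAE = Serious Adverse Events") that the listing is also confined to ITC. The footnote only expands abbreviations and the listing's title is not visible, so this is not established.
- **Section 6.3.** It can be read as ruling out any analysis beyond the descriptive summary. That is a fair reading, and a cross-reference would settle it.

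**Conclusion.** The point holds in a narrow form. By the SAP's stated rule, an AE that leads to withdrawal after procedures begin but before a first session is completed is left out of the AE summary table and its denominator. The exclusion depends on the outcome being summarized and serves no analytical purpose for AEs. It is also narrower than the protocol's undertaking to summarize AEs for all participating subjects, although that sentence concerns annual renewal reports.

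The size cannot be derived. The likely effect is small: AEs are not anticipated, and the listing included with the documents shows none. The contrast of about 1% with zero is an illustration, and a precise comparison such as 1/85 against 0/84 would assume that every other enrolled subject enters ITC. The SAP in fact allows for screening failures and withdrawals among the 85. Nor do the documents support a claim that AE rates in general are biased, since the plan sets no AE rate to be estimated.

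The conclusion assumes that the ITC sentence in 4.2.6 governs the table, that the withdrawal condition in 4.1.2 refers to the time before a first completed session, and that events during preparation count as AEs in this study.

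**What to change.** - In SAP 4.2.6, tabulate AEs in all consented subjects who began any study procedure. This is cleaner than using the All-Enrolled population, which would add screen failures with no study exposure to the denominator.
- Confirm that the AE listing covers the same set.
- In SAP 4.1.2, state that the withdrawal condition means withdrawal before a first session is completed, in line with 4.1.4.
- In SAP 6.3, replace the statement that no safety analysis is planned with a reference to the descriptive AE summary in 4.2.6.

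The cost is a few sentences in the SAP and an AE denominator that differs from ITC and needs its own label in the table header. No new data are needed, and the primary analysis is unaffected.
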